8.4. Pharmacokinetics

Blood samples will be collected in serum separator collection tubes to evaluate PK at the following visits: pre- and 6 hours (\pm 1 hour) post-injection on Day 1, prior to SC administration on Weeks 2, 4, 8, 12, 16, 20, 24, 36, 48, 52, 64, 76, 88, 100, and 104; a single sample will be collected at the End-of-Study Visit.

PK samples will be collected, processed, and stored at the site until shipment to the central laboratory. The central laboratory will store the samples at $\leq -70^{\circ}\text{C}$ until shipment to the appropriate laboratory for testing.

Instructions for processing, handling, storing, and shipping of PK samples will be detailed in a Laboratory Manual that will be provided to each site prior to site initiation.

[REDACTED]

Samples may be stored for up to 15 years after the end of the study to achieve study objectives. Additionally, with participants' consent, samples may be used for further research by sponsor or others such as universities or other companies to contribute to the understanding of LN or other diseases, the development of related or new treatments, or research methods.

8.8. Immunogenicity Assessments

Daxdilimab immunogenicity will be assessed by the incidence and titer of anti-drug antibodies prior to the daxdilimab administration and at specified time points. Number and percentage of participants who develop positive ADA will be summarized by treatment group. The potential association of ADA with safety and efficacy may be explored if data allow.

The detection and characterization of antibodies to study intervention will be performed using a validated assay method by or under the supervision of the Sponsor. Antibodies may be further characterized and/or evaluated for their ability to neutralize the activity of the study intervention. Samples may be stored for a maximum of 15 years (or according to local regulations) following the last participant's last visit for the study at a facility selected by the Sponsor to enable further analysis of immune responses to study intervention.

Instructions for processing, handling, storing, and shipping of antidrug antibody samples will be detailed in a Laboratory Manual that will be provided to each site prior to site initiation.

9. STATISTICAL CONSIDERATIONS

9.1. Statistical Hypotheses

The statistical hypotheses are as follows:

1. Null hypothesis (H_0): difference in proportion of responders (daxdilimab vs placebo) = 0
2. Alternative hypothesis (H_a): difference in proportion of responders (daxdilimab vs placebo) $\neq 0$

9.2. Sample Size Determination

A sample size of approximately 210 participants (up to approximately 70 participants per treatment group) is planned for this trial. The sample size was calculated based on the primary efficacy endpoint. Assuming a placebo response rate of 25%, 70 participants per treatment group will provide approximately 80% power to detect an increase in response of 20% in either arm of a daxdilimab group as compared to the placebo group at the 2-sided alpha level of 0.10 using a Chi-square test. The minimum detectable difference is 13% between the daxdilimab group and placebo group. The assumption of 25% responder rate for placebo is based upon published results ([Mejia-Vilet et al, 2021](#)).

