4. STUDY DESIGN

4.1. Overall Design

This trial is a Phase 2, multicenter, double-blind, randomized, placebo-controlled, parallel-group trial to assess the efficacy and safety of daxdilimab in patients with active, proliferative lupus nephritis despite standard of care. An overview of the trial design is presented in the schematic provided in Section 1.2 and details of trial activities are provided in Section 1.3.

Approximately 210 participants will be randomized in a ratio of 1:1:1 (70 participants per group) to receive either daxdilimab [REDACTED] mg or [REDACTED] mg SC or placebo SC in addition to SOC background therapy as described below in [Table 5](#). Randomization will be stratified by:

- Pre-randomization urine protein to creatinine ratio (UPCR) < 3.0 mg/mg vs. \geq 3.0 mg/mg
- Screening eGFR < 60 mL/min/1.73m² vs. \geq 60 mL/min/1.73m²

Table 5 First Year Treatment Assignment

Group	
1	[REDACTED]
2	[REDACTED]
3	[REDACTED]

Table 6 Second Year Treatment Assignment

Group	
1	[REDACTED]
2	[REDACTED]
3	[REDACTED]

Participants may enter the study taking daily OCS at a maximum dose of 0.5 mg/kg/day of prednisone-equivalent, not to exceed 40 mg/day, and must be on a stable dose for at least 10 days prior to Randomization. In addition, participants will receive IV methylprednisolone pulse 500 mg on the day of Randomization, prior to receiving the study intervention, unless they received a methylprednisolone pulse of \geq 500 mg within 10 days prior to Randomization followed by a reducing taper of OCS for participants already taking OCS prior to entry.

For participants who are not already taking prescribed MMF prior to Randomization, the dosing of MMF will start at 500 mg twice a day (BID) for a total daily dose of 1 gm/day for the first week, increasing to 1 gm BID for a total daily dose of 2 gm/day for the second and subsequent weeks (ie, beginning on Day 8). Prior to initiation of MMF, please refer to the restricted medications section in prior and concomitant therapy criteria because of potential interaction with MMF. An equivalent dose of mycophenolic acid (MPA) may be used as an alternative to MMF.

This trial will comprise a Screening Period of approximately 4 weeks (Days -28 to -1), a Treatment Period with Randomization on Day 1 followed by treatment through [REDACTED] ([REDACTED] totaling [REDACTED]
[REDACTED]
[REDACTED]

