9.4.2.2. Control of Type I Error

The type I error rate will be controlled at 0.1 level (2-sided) for the primary efficacy analysis using a fixed sequence testing procedure.

1. The primary endpoint will be tested for Daxdilimab [REDACTED] mg compared with placebo.
2. If p-value is \leq 0.1 in step 1, the primary endpoint will be tested for Daxdilimab [REDACTED] mg compared with placebo.

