4.8.1.4 Control of Type I Error

1. The type I error rate will be controlled at a 0.1 level (2-sided) for the primary efficacy analysis using a fixed sequence testing procedure. The primary endpoint will be tested for daxdilimab [REDACTED] mg compared with placebo.
2. If p-value is \leq 0.1 in step 1, the primary endpoint will be tested for daxdilimab [REDACTED] mg compared with placebo. If step 1 test is not significant, the test for Daxdilimab [REDACTED] mg will not be performed.

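### The stated 80% power for either daxdilimab arm holds only for the first-tested dose; through the fixed-sequence gate the second-tested dose has about 69% at the planned effect

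*Protocol*

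**What the plan says.** Protocol 9.2 sizes the trial on the primary endpoint, complete renal response. At a placebo rate of 25% and 70 participants per group it claims "approximately 80% power to detect an increase in response of 20% in either arm of a daxdilimab group". The basis named there is a chi-square comparison with placebo, two-sided, at alpha 0.10. The paragraph also gives a smallest detectable difference of 13 points. SAP 2.3 repeats the paragraph. The protocol synopsis gives the same power figure but refers only to a daxdilimab group, without extending it to both arms.

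Protocol 4.1 sets three equal groups with a single placebo group shared by both comparisons: "Approximately 210 participants will be randomized in a ratio of 1:1:1 (70 participants per group".

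Protocol 9.4.2.2 then fixes the order of testing: "The type I error rate will be controlled at 0.1 level (2-sided) for the primary efficacy analysis using a fixed sequence testing procedure". The second dose is tested only if the first gives p ≤ 0.1. SAP 4.8.1.4 confirms the consequence of a failed first step: "If step 1 test is not significant, the test for Daxdilimab" (dose redacted) is then not carried out. No visible section gives the power of the second step or says that the 80% leaves the sequence out of account.

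**The concern.** The sample-size paragraph attaches one power figure to both doses, but the testing rule treats them differently. The first-tested dose needs one significant result. The second needs two: its own and the first dose's. Its chance of a positive conclusion is therefore a joint probability, which cannot exceed the stand-alone figure and is visibly below it at the effect for which the trial was sized.

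At stake is how the trial is read. Someone using Protocol 9.2 to judge what the study can show about each dose would assume that they have equal chances of a formal claim. If the second-tested dose ends without one because the sequence stopped, that reader would take this as an outcome with a probability of about 20% for a truly effective dose. Under the plan's own assumptions it is closer to 31%.

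**Working it through.** **Inputs.** Protocol 9.2: placebo rate 25%; daxdilimab rate 25% + 20 points = 45%; chi-square test; two-sided alpha 0.10 (critical value 1.645). Protocol 4.1: 70 per group, shared placebo group. Protocol 9.4.2.2 and SAP 4.8.1.4: second dose tested only after p ≤ 0.1 for the first.

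**Step 1: reproduce the stated power.** For one comparison, with p̄ = (0.25 + 0.45)/2 = 0.35:

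- Standard error under the null = √(2 × 0.35 × 0.65 / 70) = 0.0806
- Standard error under the alternative = √((0.25 × 0.75 + 0.45 × 0.55) / 70) = 0.0788
- Power = Φ[(0.20 − 1.645 × 0.0806) / 0.0788] = Φ(0.855) = 80.4%

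Exact enumeration of the uncorrected chi-square test also gives 80.4%. The minimum detectable difference reproduces too, at 12.9 points for an observed placebo rate of 25%. Both stated figures are therefore correct for a single ungated comparison.

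**Step 2: put the second dose through the gate.** Let A₁(c) and A₂(c) be the probabilities that dose 1 and dose 2 are significantly better than placebo when the placebo group has c responders. The overall power for the second-tested dose is

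Σ over c of Bin(c; 70, 0.25) × A₁(c) × A₂(c).

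The sum over the shared placebo count carries the positive correlation between the two comparisons: (0.25 × 0.75)/(0.25 × 0.75 + 0.45 × 0.55) = 0.1875/0.435 = 0.43 when both doses are at 45%.

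With both doses at +20 points, exact enumeration gives 69.2%. A bivariate normal approximation gives 68.5%. Ignoring the correlation would give 0.804² = 64.6%, which is too low.

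**Step 3: vary the first-tested dose, holding the second at a true rate of 45%** (exact enumeration):

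| True effect of first-tested dose | Power, first dose | Overall power, second dose |
|---|---|---|
| +10 points | 36.8% | 34.6% |
| +15 points | 60.4% | 54.3% |
| +20 points (planned) | 80.4% | 69.2% |
| +25 points | 92.7% | 76.9% |
| +30 points | 98.1% | 79.6% |

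**Step 4: locate the loss.** At +20/+20 the shortfall is 80.4% − 69.2% = 11.2 points. These are the trials in which the second dose would have been significant but the first was not, so the second is never tested. Power given that the second dose is tested is 69.15/80.37 = 86% at +20/+20, and 54.35/60.35 = 90% if the first dose is at +15. Both exceed 80%, because passing the first step makes a low placebo result more likely.

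**The case against.** The strongest reply is that per-comparison power is the usual basis for sizing and that Protocol 9.2 names its basis: one arm against placebo, chi-square, alpha 0.10. On that reading the 80% is right for each contrast, and the paragraph makes no claim about the sequence. The either-arm wording could also mean that at least one dose succeeds; under the fixed sequence that probability equals the first-step power, again 80%. Both readings explain where the figure comes from, and they rule out a calculation error. They do not rescue the sentence. Nothing visible tells the reader that the sequence has been set aside, and the ordinary sense of the wording covers the second dose as well.

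Three further points stand.

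- The rows with a weaker first dose assume that the second-tested dose is truly the better one. The order is redacted, so their plausibility cannot be judged; only the +20/+20 row uses the plan's own effect.
- The primary analysis is a logistic regression adjusted for baseline eGFR and UPCR (Protocol 9.4.2.1, SAP 4.8.1.2). There is also a non-binding futility analysis whose details are redacted. The 69% reflects neither.
- The practical effect is modest. This is a Phase 2 trial, the error control is valid, and nothing says that a failed first step withholds the estimated difference and its 90% interval for the second dose.

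**Conclusion.** The stated power is not delivered for one of the two arms. It is about 80% for the first-tested dose and about 69% for the second-tested dose when both have the planned 20-point effect, a gap of about 11 points. This rests on the plan's own rates, 70 per group, an unadjusted chi-square test and no futility stop. It does not depend on which dose is tested second.

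Three stronger conclusions that a reader might draw are not supported.

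- **That 69% is a ceiling.** It is the value at one scenario. Overall power for the second dose is 77% if the first dose's effect is 25 points and almost the full 80% if it is 30.
- **That the 80% was miscalculated.** It reproduces; the fault is in extending it to the second arm without the testing rule.
- **That a second dose which is tested and found not significant had too little power.** Given that it is tested, its power is about 86% at the planned effects. The shortfall lies wholly in the second dose going untested, an outcome that SAP 4.8.1.4 openly provides for.

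**What to change.** In Protocol 9.2 and SAP 2.3, replace the either-arm claim with wording such as: about 80% power for the first-tested dose; about 69% for the second-tested dose under the fixed-sequence procedure if both doses have a 20-point effect, and lower if the first-tested dose has a smaller effect (unadjusted chi-square, ignoring any futility stop).

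The cost is one sentence in each document and a less favourable published figure for the second dose. Sample size, test, alpha and testing order stay as they are. For scale, bringing the second-tested dose to about 80% at +20/+20 would take about 90 per group (exact 80.8%), or 270 in total against the planned 210. The correction does not require that.

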9.3. Analysis Sets

Analysis Populations:

Full Analysis Set: The Full Analysis Set will include all randomized participants who receive any dose of study intervention in the study. Participants will be analyzed according to the treatment randomized. The efficacy analysis will be based on the Full Analysis Set.

Safety Analysis Set: The Safety Analysis Set will include all participants who receive any dose of study intervention in the study. Participants will be analyzed according to the treatment that they actually received. Safety, PD, and ADA analyses will be based on Safety Analysis Set.

PK Analysis Set: The PK Analysis Set will include all participants who receive any dose of daxdilimab in the study and have at least one quantifiable serum PK observation post first dose. Participants will be analyzed according to the treatment that they actually received. The PK analysis will be based on the PK Analysis Set.

9.4. Statistical Analyses

9.4.1. General Considerations

Continuous variables will be summarized in tables and will include the number of participants, mean, standard deviation (SD), median, minimum, and maximum. Categorical variables will be presented in tables as frequencies and percentages. Details of the statistical analysis will be specified in a separate SAP.

9.4.2. Primary Endpoint Analysis

9.4.2.1. Analyses of the Primary Efficacy Endpoint:

The estimand of primary interest is defined as follows, using composite variable strategy to address intercurrent events.

1. Population: Participants in the Full Analysis Set.
2. Variable (outcome measure): CRR at [REDACTED]. CRR is defined by meeting the following criteria:
 - a. eGFR \geq 60 mL/min/1.73m² or no worse than 15% below baseline.
 - b. 24-hour UPCR \leq 0.5 mg/mg.
 - c. No use of restricted medication beyond the protocol allowed threshold before assessment.
 - d. No discontinuation of study intervention.
3. Intercurrent event:
 - a. Rescue medications: Captured in the primary variable definition.
 - b. Treatment discontinuation: Captured in the primary variable definition.
4. Population-level summary: Difference in proportions of responders between the daxdilimab group and placebo group.

The proportion of participants achieving CRR at [REDACTED] in the daxdilimab group will be compared to that of the placebo group using a logistic regression model with treatment, baseline eGFR value and baseline UPCR value included in the model. The difference in proportions of responders of daxdilimab vs placebo will be estimated together with its associated 2-sided 90% confidence interval (CI).

9.4.2.2. Control of Type I Error

The type I error rate will be controlled at 0.1 level (2-sided) for the primary efficacy analysis using a fixed sequence testing procedure.

1. The primary endpoint will be tested for Daxdilimab [REDACTED] mg compared with placebo.
2. If p-value is \leq 0.1 in step 1, the primary endpoint will be tested for Daxdilimab [REDACTED] mg compared with placebo.

9.4.3. Secondary Endpoints Analysis

The estimand for the binary secondary efficacy endpoints is defined as follows, using composite variable strategy to address intercurrent events.

1. Population:
 - a. ORR: Participants in the Full Analysis Set.
 - b. Sustained reduction of OCS dose: Participants in the Full Analysis Set whose Baseline OCS dose is greater than 2.5 mg/day prednisone equivalent.
2. Variable (outcome measure):

- a. ORR at [REDACTED] which is an CRR or PRR at Week 52. PRR is defined by meeting the following criteria:
 - i. eGFR ≥ 60 mL/min/1.73m² or no worse than 15% below baseline.
 - ii. Improvement in 24-hour UPCR:
 - For participants with a baseline UPCR ≤ 3.0 mg/mg: < 1.0 mg/mg
 - For participants with a baseline UPCR > 3.0 mg/mg: $> 50\%$ improvement from baseline and ≤ 3.0 mg/mg
 - iii. No use of restricted medication beyond the protocol allowed threshold before assessment.
 - iv. No discontinuation of study intervention.
- b. Response in sustained reduction of OCS dose, which is defined by meeting the following criteria:
 - i. Prednisone-equivalent dose ≤ 2.5 mg/day by Week 24 and not exceeding this dose through Week 52.
 - ii. No use of restricted medication beyond the protocol allowed threshold before assessment.
 - iii. No discontinuation of study intervention.
3. Intercurrent event:
 - a. Rescue medications: Captured in the variable definition.
 - b. Treatment discontinuation: Captured in the variable definition.
4. Population-level summary: Difference in proportions of responders between the daxdilimab group and placebo group.

ORR will be analyzed using a logistic regression model with treatment, baseline eGFR value and baseline UPCR value included in the model. Response in sustained reduction of OCS dose will be analyzed similarly using a logistic regression model with treatment, randomization stratification factors and baseline OCS dose included in the model.

The estimand of change from baseline in eGFR at Week 52 is defined as follows, using hypothetical strategy to address intercurrent event of rescue medications and treatment policy strategy to address intercurrent event of treatment discontinuation.

1. Population: Participants in the Full Analysis Set.
2. Variable (outcome measure): Change from baseline in eGFR at Week 52.
3. Intercurrent event:
 - a. Rescue medications: The data collected after administration of the rescue medications will be excluded.
 - b. Treatment discontinuation: Participants who discontinue study intervention will be asked to come to scheduled evaluations until the end of study. The data collected after discontinuation of study intervention will be included in the analysis.

2. The population-level summary: Mean difference between the daxdilimab group and placebo group.

Change from baseline in eGFR will be analyzed using mixed models for repeated measures (MMRM) with treatment, visit, visit by treatment interaction, randomization stratification factor (UPCR only), and baseline eGFR value included in the model.

[REDACTED]

[REDACTED]

[REDACTED]

9.4.5. Handling Plan for Missing Data:

For the categorical endpoint, the intermittent missing data will be imputed using last observation carried forward approach (LOCF). Participants with missing outcomes due to early discontinuation from the study will be considered as non-responders. If any of the criteria cannot be evaluated at a visit, that criterion will be imputed using LOCF. For the continuous endpoint, the missing data will be handled using the MMRM approach.

9.4.6. Safety Analyses

AEs will be coded using the most recent version of Medical Dictionary for Regulatory Activities (MedDRA). Treatment emergent AEs will be summarized by the number of participants reporting the events, as well as by System Organ Class, Preferred Term (PT), severity, seriousness, and relationship to study intervention. For the summary of AEs by severity, each participant will be counted only once within a System Organ Class or a PT by using the AEs with the highest intensity within each category. For the summary of AEs by relationship to study intervention, each participant will be counted only once within a System Organ Class or a PT by using the AEs with the greatest reported relationship within each category. The number and percentage of participants reporting treatment-emergent SAEs and treatment-emergent AESIs will also be summarized.

Clinically significant changes in laboratory analyses, vital signs, ECGs, and new findings on physical examination will be recorded as AEs or SAEs. Laboratory assessments, vital signs, and ECGs, as well as their changes from Baseline at each visit will also be summarized descriptively.

9.4.7. Pharmacokinetic Analyses

Serum concentrations will be summarized descriptively by treatment and by visit and the mean (\pm SD) serum concentration versus scheduled time profiles will be presented graphically.

Individual serum concentration vs. actual time profiles for each participant will be listed.

[REDACTED]

9.4.9. Planned Analyses

Term	Percentage
GMOs	~85%
Organic	~95%
Natural	~90%
Artificial	~80%
Organic	~95%
Natural	~90%
Artificial	~80%
Organic	~95%
Natural	~90%
Artificial	~80%

9.4.9.2. Planned Primary Analysis

The primary analysis will be conducted after the last participant has completed the Week 52 Visit or discontinued from study early. For the primary analysis, all the efficacy and safety data collected prior to the data cut-off will be analyzed.

9.4.9.3. Planned Final Analysis

The final analysis will be conducted after all participants have completed Week 112 Visit or discontinued early from the study.

10. REGULATORY, ETHICAL, AND TRIAL OVERSIGHT CONSIDERATIONS

10.1. Local Regulations/Declaration of Helsinki

This trial will be conducted in accordance with the ethical principles that have their origin in the Declaration of Helsinki and that are consistent with ICH Tripartite Guideline for GCP and the applicable laws and regulations of the country in which the research is conducted, whichever affords greater protection to the individual.

10.2. Ethical Review

It is the understanding of the Sponsor that this protocol (and any amendments) as well as appropriate consent procedures, will be reviewed and approved by a research ethics board (REB)/institutional review board (IRB). This board must operate in accordance with the current federal regulations. For sites with a local ethics committee, a letter or certification of approval will be sent by the Investigator to the Sponsor (or CRO) before initiation of the trial and also whenever subsequent modifications to the protocol are made.

